3.3. Expected Duration of Treatment and Subject Participation

Each course of radiation therapy will be 3-5 fractions delivered over 3-21 days. The first course of radiation will be initiated at any time point between the date of cycle 1 of immune therapy through the date of cycle 2 of immune therapy. The duration of immune therapy administration and the number of courses of radiation therapy that a subject receives will be dependent upon the subject's response to prior treatment. There is no specific maximum number of cycles of immune therapy if a patient continues to respond to treatment, or courses of radiation therapy if a patient has persistent stable disease on imaging. Progressive disease will be defined per irRC criteria as assessed by two imaging studies \geq 4 weeks apart. Because abscopal responses have been reported even when the radiation is given after the immune therapy was completed, a final course of radiation therapy will be offered to patients at the time of progressive disease on imaging.³⁸⁻³⁹ Subsequent therapy decisions will be at the discretion of the treating physicians, including the option of continuing the immune therapy past progression if clinically indicated.

The radiation therapy or immune therapy may be cancelled or discontinued at any point if no longer medically advisable due to intercurrent illness, toxicity/adverse event, decline in performance status, pregnancy, the best interests of the patient, or death. Subjects may also withdraw consent from treatment (partial consent) or from the study (full consent).

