5.3. Subsequent Response-Adapted Radiation Therapy

Any patient who completes the initial course of radiation therapy and continues on one of the immune checkpoint inhibitors described above will be eligible for subsequent course(s) of radiation therapy to a different lesion that was not previously irradiated based on the results of follow-up imaging studies detailed below and in section 11.

- Patients with a partial or complete response per irRC criteria will be observed without any further radiation therapy until progression.
- Patients with stable disease per irRC criteria will undergo an additional course of radiation therapy given concurrently with the next cycle of immune checkpoint

- therapy, and then continue the immune therapy as above. Each subsequent course of radiation therapy should ideally be at least 2 months after completion of the prior course of radiation therapy, but is left at the discretion of the treating physician depending on the patient's palliative needs. Day 1 of radiation should be on Day 1 of the next cycle of immune therapy.
- Patients with progressive disease at any time per irRC criteria will undergo a final course of radiation therapy. This may be given concurrently with a final cycle of immune therapy or as stand-alone treatment within 6 weeks after discontinuation of immune therapy but before an alternative systemic therapy is initiated.

Please see Section 5.5 below regarding situations in which these subsequent courses of radiation therapy may be withheld. Each subsequent course of radiation therapy should be given in a similar style as detailed for the initial course of radiation therapy above. In patients with a mixed response to therapy, preference will be given to an enlarging tumor (rather than one that is stable or decreasing in size) as the site of treatment. Reimaging will again be obtained after completion of the radiation therapy with timing at the discretion of the treating physicians, and the same response-adapted approach to decision making for further courses of radiation therapy will be carried out as described above.

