13.3. Methods for Analysis

Data will be summarized with respect to baseline characteristics and safety measurements using descriptive statistics (quantitative data) and contingency tables (qualitative data). The safety analysis will consist of AE summaries (frequency tables based on CTCAE grades) and laboratory abnormalities summary. For the primary endpoint, the response rate and its 95% confidence interval will be estimated with a binomial distribution. Univariate and multivariate logistic regression model will be used to assess the association between response and several radiotherapy variables (biologic effective dose,

number of lesions treated, sequence of radiation and immune therapy), tumor variables (irradiated tumor site, size, growth rate, histology, PD-L1 status, local response, extent of prior chemotherapy use, and biologic correlates), and patient variables (age, smoking status, and other factors associated with secondary immunodeficiency). A predictive nomogram for response will be developed based on the outcome of the multivariate analysis. In the data analysis on the secondary endpoints, the Kaplan-Meier method will be used to estimate overall survival and progression-free survival. Wilcoxon signed-rank test for paired data will be used to assess the change of quality of life scores between two visits. Since the lung cancer score (LCS) of the FACT-L focuses on lung cancer symptoms, this will be used for the primary QOL endpoint; however, the more general subscales of physical and functional well-being on the Trial Outcome Index (FACT-TOI) will also be collected. A difference of 3 LCS points will be considered clinically significant.¹²⁻¹³ Where applicable, comparison will be made to previous randomized trials assessing immune checkpoint inhibitors alone in a comparable patient population.

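### Section 13.3 uses the number of lesions treated to predict response, but Section 5.3 makes that count partly a consequence of response status; the nomogram built from the model also has no optimism correction

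*Combined protocol and SAP*

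**What the plan says.** Section 13.3 (Methods for Analysis) plans univariate and multivariate logistic regression of response on radiotherapy, tumor and patient variables. The radiotherapy group is biologically effective dose (BED) followed by "number of lesions treated, sequence of radiation and immune therapy". The multivariable result then feeds a predictive nomogram. The section does not define the lesion count. It plans no landmark, time-dependent or first-course analysis and no internal validation.

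Section 5.3 ties later courses to imaging response:

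- Response: "Patients with a partial or complete response per irRC criteria will be observed without any further radiation therapy until progression".
- Stable disease: "Patients with stable disease per irRC criteria will undergo an additional course of radiation therapy".
- Progression: "Patients with progressive disease at any time per irRC criteria will undergo a final course of radiation therapy".

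Each later course goes "to a different lesion that was not previously irradiated", so each one raises the count. Section 3.3 sets no maximum number of "courses of radiation therapy if a patient has persistent stable disease on imaging". It describes the last course less firmly than 5.3 does ("a final course of radiation therapy will be offered to patients at the time of progressive disease on imaging") and adds that "The radiation therapy or immune therapy may be cancelled or discontinued at any point if no longer medically advisable".

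Best overall response is taken from the start of treatment to progression (11.2.1). The synopsis and Section 1.2 list number of fractions and duration of radiotherapy among the predictors, and neither lists lesion count. The synopsis calls the predictor analysis exploratory, 1.2 places it under secondary objectives, and 13.1 does not list it.

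**The concern.** A predictor of response should be fixed before response is known. A cumulative lesion count is not. Staying in stable disease adds lesions by rule, and responding stops the additions until progression. An association between more lesions and less response can therefore arise from the treatment rule alone. Repeated, response-adapted radiation is the strategy the trial is named for, so such a result could be reported as evidence about that strategy.

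Local response is in the same list. It is assessed on the same follow-up scans as systemic response (11.1.1), so it is an outcome and not a baseline predictor.

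A separate risk is that a nomogram fitted to very few responders, with no correction, looks discriminating when it is not.

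**Working it through.** **1. The plan's own figures.** An exact search for Simon's minimax design at 20% versus 40%, alpha 0.05 and 80% power returns 18 patients in stage one (boundary 4 responses), 33 in total and a final cut-off of 10. Early termination probability is 0.716 (Section 13.2 states 0.72), alpha 0.0458 and power 0.801. The 33 patients and the two rates are therefore sound inputs.

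**2. Lesion count with no effect of radiation.** The documents give no scan-by-scan rates, so these are assumptions: four scans; 20% respond and 35% progress at the first; among those still stable, 10% respond and 35% progress at each later scan; at most five lesions. The stable fraction is 45% at scan 1, then 55% of those remaining.

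| | Scan 1 | Scan 2 | Scan 3 | Scan 4 |
|---|---|---|---|---|
| Responds | 0.2000 | 0.0450 | 0.0248 | 0.0136 |
| Progresses | 0.3500 | 0.1575 | 0.0866 | 0.0476 |
| Lesions treated by then | 1 | 2 | 3 | 4 |

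A further 0.0749 are stable throughout, with 5 lesions. Overall response is 0.2834, inside the plan's 20 to 40%.

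Counting only courses before progression:

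- Responders: (0.2000×1 + 0.0450×2 + 0.0248×3 + 0.0136×4) / 0.2834 = 1.48.
- Non-responders: (0.3500×1 + 0.1575×2 + 0.0866×3 + 0.0476×4 + 0.0749×5) / 0.7166 = 2.08.

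If every patient who progresses takes the final course and every responder eventually progresses, responders gain 1 (2.48). Non-responders gain 0.6417/0.7166 = 0.90 (2.97). The gap remains under either way of counting.

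**3. What 33 patients would show.** Simulation at these rates, 4,000 trials per setting, with the same final-course uptake in responders and non-responders:

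| Final-course uptake | 0% | 50% | 80% | 100% |
|---|---|---|---|---|
| Negative coefficient | 93% | 90% | 90% | 91% |
| Logistic likelihood-ratio p<0.05 | 27% | 22% | 22% | 26% |
| Logistic Wald p<0.05 | 4% | 10% | 8% | 5% |

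A pure-noise baseline covariate gives 7% (likelihood-ratio) and 4% (Wald). Section 13.3 does not say which test is used.

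**4. How far this moves.**

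- Over 18 sets of rates and four equal uptakes, with up to five lesions, false positives run from 5 to 93% (likelihood-ratio) and 0 to 77% (Wald). Five of the 18 sets imply overall response outside 20 to 40%.
- Unequal uptake matters. By rank-sum test, which is not the planned analysis, 100% in responders and 70% in non-responders gives 3.5%; 60% and 80% gives 32%.
- A separate run took 1,500 random scenarios with overall response of 20 to 40% and the response duration of 12.5 to 17.0 months from Section 2.2. With 12 to 24 months of follow-up (one-year accrual in a two-year study, 13.2), responders had fewer lesions in 98.6% of scenarios (median difference −0.69). With follow-up until everyone progresses (3.5), they had fewer in 71%, about equal in 5% and more in 23% (median −0.20).
- A reversal: 8% respond and 45% progress at the first scan, then 20% and 35%, with full uptake and complete follow-up. Mean lesions are 3.23 in responders and 2.72 in non-responders.

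**5. Nomogram.** Section 13.3 names 3 radiotherapy, 7 tumor and 2 patient items, 12 in all, plus two open groups. Expected responders are 33×0.20 = 6.6 to 33×0.40 = 13.2. Per named covariate that is 6.6/12 = 0.55 to 13.2/12 = 1.10. Counting each open group as one gives 6.6/14 = 0.47 to 13.2/14 = 0.94. With pure-noise covariates, whose true AUC is 0.50, the mean apparent AUC is:

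| Model | 7 responders | 13 responders |
|---|---|---|
| All 12 fitted | 0.94 | 0.87 |
| 12 screened at p<0.10 | 0.80 | 0.76 |
| 3 prespecified | 0.70 | 0.67 |
| 3 prespecified, bootstrap-corrected | 0.58 | 0.55 |

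**6. Which landmark set is safe.** Use the step 2 rates and assume 70% of stable patients get a second course. Patients stable at scan 1 number 33×0.45 = 14.9, and their later response is (0.0450 + 0.0248 + 0.0136)/0.45 = 18.5%, treated or not. If the set is instead everyone not yet in response, it has 33×0.80 = 26.4 patients, including 33×0.35 = 11.6 who have already progressed and can no longer respond under 11.2.1. Expected responders are 10.4×0.185 = 1.92 among treated stable patients and 4.5×0.185 = 0.83 among untreated ones. With full final-course uptake, response is 1.92/(10.4 + 11.6) = 8.7% in treated against 18.5% in untreated. With none, it is 18.5% against 0.83/(4.5 + 11.6) = 5.2%. The wider set brings the artefact back in either direction.

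**The case against.** Four points are fair.

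- **The count is undefined.** Section 13.1 words the endpoint as response after the initial course. Sections 2.4 and 5.1.2 advise treating a visceral metastasis alongside a bone or brain one, so a course can cover more than one lesion. Counted within the first course, the variable is not driven by response. Against this, 3.1 speaks of one target lesion at the start, which would leave such a count almost constant. This stands as a reason to define the variable and not simply to ban it.
- **The size is assumed.** Base-case Wald error is near nominal at two of four uptakes, and a positive difference is possible. This stands. A reader might infer that the analysis is bound to produce a significant negative finding, and the documents do not support that.
- **The ratio of 0.55 to 1.10 assumes that all 12 covariates enter.** Section 13.3 does not say so, and the p<0.10 screen is only an illustration. The missing selection rule is mainly missing detail. The missing optimism correction remains, because even three prespecified noise covariates look better than chance.
- **The biomarker point is thin.** Sections 9.1.2 and 9.2.2 feed levels from before and during therapy into the same model, and later samples are tied mainly to a change in response (calendar note 17). A reader might infer that response determines the biomarker values. The documents fix only when blood is drawn. The separate t-test of biomarkers by response in 13.2 is not in question.

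None of this rescues a cumulative count as a predictor. Restricting it to courses before progression does not help either, as step 2 shows.

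**Conclusion.** The concern holds in a limited form. A cumulative number of lesions treated depends on response status through Section 5.3, so its coefficient does not estimate an effect of treating more lesions, whatever its sign. With no true effect the lean is usually negative. Its magnitude, and occasionally its direction, rest on scan-by-scan rates, follow-up and final-course uptake that are assumed here. The simulations do not model the discretionary timing of later courses or the organ-dose limits on repeat courses.

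Local response does not belong in a predictive model for the same basic reason: it is observed after baseline. The nomogram would rest on 6.6 to 13.2 expected responders, fewer if the trial stops at stage one or some patients are not evaluable, and its apparent performance would be inflated.

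A reader might extend this to the trial's main conclusions. That does not follow: the analyses of the primary response rate, PFS, OS, safety and quality of life do not use this model.

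**What to change.** In Section 13.3, with matching wording in 9.1.2 and 9.2.2:

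1. Limit predictors of response to values fixed by the first course (BED, number of fractions, duration, irradiated site, timing relative to cycle 1 and, if wanted, number of lesions treated in that course), baseline tumor and patient variables, and baseline biomarkers. This also brings 13.3 into line with the synopsis and 1.2 on fractions and duration.
2. Remove the cumulative lesion count from the model and describe later courses only. If a landmark analysis is added, restrict it to patients with stable disease at the first response assessment, excluding those who have already progressed. State that it has little power (about 15 patients under the assumed rates) and is confounded: 5.3 has all stable patients receive another course, so those who do not will differ from those who do.
3. Report local response and on-therapy biomarkers as associations with systemic response, outside the predictive model. The correlation with local response in 1.2 and the t-test in 13.2 stay.
4. Label any nomogram hypothesis-generating, build it from a few covariates named before data lock, and report bootstrap optimism-corrected AUC and calibration. Otherwise drop it.

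The cost is wording. No treatment rule changes and no new data are needed: dose, fractions and dates of each course are already recorded (6.1, 10.1.2), and calendar note 13 adds lesion location. The price is a more limited nomogram and only descriptive results for later courses. At this sample size bootstrap correction removes most of the optimism but not all of it.

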1.2. Secondary Objective(s)

To determine 1-year progression-free survival (PFS); 1-year overall survival (OS); safety/toxicity using CTCAE v4.0 until 30 days after the last dose of immune therapy or until the patient begins a new cancer-directed therapy, or death, whichever comes first; quality of life using FACT-L and FACIT Fatigue Scale at 3 month intervals until the time of systemic disease progression. In order to determine factors predictive of response to therapy, we will correlate the presence of response with radiotherapy variables (biologic effective dose, number of fractions, duration of radiotherapy, sequence of radiation and immune therapy), tumor variables (irradiated tumor site, size, histology, PD-L1 status, local response, extent of prior chemotherapy use), and patient variables (age, smoking status, and biologic correlates).

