10.2. Study Calendar

Parameters	≤28 days prior to registration	Day 1 of immune therapy	Last day of first course of RT	Follow-up before documented progressive disease, at 3, 6, 9, and 12 months after initial cycle of immune therapy ¹	Follow-up before documented progressive disease, beyond 12 months after initial cycle of immune therapy is timed per standard of care at treating physicians' discretion	Follow-up after progressive disease or switch to alternative systemic therapy ²
Informed Consent	X					
Demographics	X					
History and Physical Exam	X ³			X ¹⁵	X	
Wt/Vitals/ ECOG PS	X			X ¹⁵	X	
Concomitant Med Assessment	X			X ¹⁵		
FACT/FACIT Questionnaire ⁴		X		X ¹⁵		
Serum CBC/diff/platelets ⁵	X			X ²		
Serum chemistries ⁶	X			X ²		
Serum liver function tests ⁷	X			X ²		
Serum TSH	X			X ²		
Urinalysis with reflex culture	X					
Serum β-hCG ⁸	X					
Hemoglobin A1c ⁹	X					
MRI (preferred) or CT brain with IV contrast	X					
FDG-PET/CT (preferred) or CT chest/abdomen/pelvis with IV contrast ¹⁰	X			X ¹⁶	X	
Research blood sample ¹¹		X		X ¹⁷	X ¹⁷	
Immunotherapy Administration Assessment ¹²		X	X	X	X	
Radiation Therapy Administration Assessment ¹³			X	X	X	
Survival assessment ¹⁴						X
AE/SAE Assessment ¹⁹	X	X	X	X	X	
PD-L1 status ²⁰	X					
Rebiopsy (optional)				X ¹⁸	X ¹⁸	X ¹⁸

¹The final formal assessment will be at time of documented disease progression.

²To be performed according to standard of care.

³To be documented by treating radiation oncologist. Vital signs to include blood pressure, pulse, respiratory rate, and temperature

⁴See [Appendix C](#) for questionnaires, which will be administered electronically using REDCap. A research assistant will open the questionnaire weblink (<http://j.mp/2eLzfjE>) on a password protected tablet computer, enter the patient's study ID into the survey instrument, and then the patient will complete the rest of the electronic form and submit it. The research assistant will be available to answer any questions that the patients have, if necessary. Details on REDCap can be found in Section 12.1 below. The initial questionnaire may be done anytime between signing the consent and the first immune therapy treatment. The questionnaires may be completed using paper forms if REDCap is unable to be accessed or based on patient preference.

⁵CBC with differential includes hemoglobin, hematocrit, white blood cell count, absolute neutrophil count, and platelets

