13.2. Sample Size/Accrual Rate

The primary analysis will be for patients enrolled at time-points (A) and (B) above, whereas patients enrolled at time-point (C) will be included in observational analysis only (see section 3.1). The primary endpoint of this study is the overall response rate (complete + partial response) and the efficacy will be assessed using the Simon's two-stage Minmax design. A sample size of 33 patients is chosen to differentiate between the response rate of 20% and 40% with 80% power at a significance level of 0.05. In particular, 18 patients will be enrolled at the first stage. If 15 or more of the first 18 patients have disease progression prior to any response, the trial will be terminated; otherwise an additional 15 patients will be treated for a total of 33 patients. In the final data analysis, if 10 or fewer patients respond among 33 patients, the treatment will be concluded ineffective. The probability of early termination due to futility is 0.72.

For correlative study between biomarkers and response, this sample size will have at least 80% power to detect a 50% change/difference on biomarker data between response and non-response groups using a two-sided two-sample t-test at 0.05 significance level, assuming that the response rate is 35% or higher and the coefficient of variation (CV) of biomarkers is 0.45.

Approximately 100 patients with metastatic NSCLC are diagnosed and treated each year at our institution, many of whom will be candidates for immune checkpoint therapy. As such, we expect to accrue 3 patients per month to this trial for an estimated accrual period of one year. The full estimated duration of the study is two years.

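### Quality of life: the two visits compared by the paired test are not named, and complete pairs at later visits leave out patients who have progressed or died

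*Combined protocol and SAP*

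**What the plan says.** Section 13.3 specifies one inferential method for QOL: "Wilcoxon signed-rank test for paired data will be used to assess the change of quality of life scores between two visits". Of the LCS it says "this will be used for the primary QOL endpoint", and it adds that "A difference of 3 LCS points will be considered clinically significant". The scale and the clinical threshold are therefore fixed in advance; the visits are not. The section gives no significance level or multiplicity rule for QOL, no longitudinal model, and no rule for missing forms, progression or death.

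Section 1.2 sets the collection period: "quality of life using FACT-L and FACIT Fatigue Scale at 3 month intervals until the time of systemic disease progression". The calendar in Section 10.2 marks FACT/FACIT in two columns only. One is Day 1 of immune therapy, with a footnote that "The initial questionnaire may be done anytime between signing the consent and the first immune therapy treatment". The other is headed "Follow-up before documented progressive disease, at 3, 6, 9, and 12 months after initial cycle of immune therapy". Nothing is marked in the column beyond 12 months or in the column after progression. Footnote 1, attached to the 3-to-12-month column, places the last formal assessment at documented progression.

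**The concern.** The calendar gives five scheduled scores per patient: baseline and months 3, 6, 9 and 12. The plan compares two of them without saying which, so the contrast behind the QOL statement can be settled after the data are seen.

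The composition of the pairs matters separately. A paired test needs both scores. Once a patient progresses or dies, later scheduled forms are not due, so each later pair describes only patients still progression-free. If patients who progress early also tend to lose more LCS points, the mean change among the rest will look better than the change in everyone enrolled. At stake is whether the LCS result, read against the 3-point threshold, describes the treated population or only those who stayed on schedule.

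**Working it through.** The documents give no power, significance level or expected number of pairs for QOL, so there is no stated figure to reproduce.

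**1. Choosing the visit pair afterwards**

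Inputs: five scheduled assessments (Section 10.2); a two-sided 5% level (assumed for QOL; Section 13.2 uses 0.05 for its own tests); no true change.

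- Possible pairs: 5 × 4 / 2 = 10, of which 4 are baseline against a follow-up visit.
- If the four tests were independent: 1 − 0.95^4 = 0.185.
- The tests share the baseline score and are correlated, so this is too high. Simulated signed-rank tests on five equally correlated visits (n = 33 and n = 20, correlation 0.3, 0.5 and 0.7, 20,000 runs each) give:

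| Contrast | Chance of at least one p<0.05, either direction |
|---|---|
| One pair named in advance | 0.046-0.049 |
| Any of the 4 baseline pairs | 0.152-0.158 |
| Any of all 10 pairs | 0.287-0.296 |

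Counting only false improvements (paired t, n = 20, correlation 0.5), the chance is about 0.08 for the four baseline pairs and 0.18 for all ten.

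**2. Patients left in the later pairs**

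The documents give no expected PFS. Assume exponential PFS with a median m of 3 to 12 months. The number still progression-free at month t is 33 × 0.5^(t/m).

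| Visit | m = 3 months | m = 12 months |
|---|---|---|
| Month 3 | 16.5 | 27.7 |
| Month 6 | 8.2 | 23.3 |
| Month 9 | 4.1 | 19.6 |
| Month 12 | 2.1 | 16.5 |

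**3. How large the selection could be**

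All inputs here are assumptions: true mean LCS change 0, SD of change 5, and correlation r of 0.3 to 0.5 between LCS change and progression time on a normal scale. With S = 0.5^(t/m) the share still progression-free, and z the normal point with upper tail S, the mean change among those remaining is 5 × r × φ(z)/S.

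- Month 3, m = 12, r = 0.3: S = 0.841, φ(z)/S = 0.288, mean = 5 × 0.3 × 0.288 = +0.4.
- Month 3, m = 3, r = 0.5: S = 0.5, φ(z)/S = 0.798, mean = 5 × 0.5 × 0.798 = +2.0.
- Month 12, m = 12, r = 0.3: S = 0.5, mean = 5 × 0.3 × 0.798 = +1.2.
- Month 12, m = 3, r = 0.5: S = 0.0625, φ(z)/S = 1.968, mean = 5 × 0.5 × 1.968 = +4.9.

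The illustration therefore runs from +0.4 to +2.0 points at month 3 and from +1.2 to +4.9 at month 12, with no true change. At r = 0 it is zero at every visit.

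**4. Whether a model on all scores helps**

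In a further simulation, dropout was driven by decline from baseline (assumed) and the score at progression was observed. The complete-pair estimate at month 12 was about +3 to +4 points too favourable. A likelihood model using all scores, including the one at progression, reduced this to about +0.2 to +0.3. Without the progression score the model helped only partly, and it did worse when dropout followed an unobserved current score.

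**The case against.** Several points on the other side stand.

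- **Other visits are not necessarily discarded.** A reader might infer that one pair will be tested and the rest dropped. The text does not say so; the sentence can equally mean a paired test at each follow-up visit. What is missing is which comparison carries the conclusion.
- **The ten-pair figure is not the right size.** A reader might quote the 29-30%. It includes contrasts such as month 6 against month 9 that nobody is likely to choose. Even the 15-16% counts deteriorations as well as improvements. The fixed LCS scale and 3-point threshold also limit what an isolated p-value can support.
- **A score at progression may exist.** Footnote 1 sits on the column where FACT/FACIT is marked, and progression under Sections 3.3 and 11.2 needs two observations at least 4 weeks apart, so some worsening may be captured. But Section 13.3 gives that form no place in a two-visit test, and nothing is scheduled after it.
- **QOL until progression is a legitimate question.** Section 1.2 states it as the objective. Results among progression-free patients are interpretable if labelled as such and shown with their numbers.
- **A mixed model is not a complete answer.** It assumes missing at random, whereas the worry is informative dropout. Counting progression as QOL worsening also overlaps with PFS. Both limits are carried into the fix.

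**Conclusion.** The point holds in a limited form. The visits are unnamed, which leaves a 15-16% chance of a nominally significant result somewhere among the four baseline pairs under no change, assuming 5% two-sided tests and equally correlated visits. Complete pairs at later visits exclude patients who have progressed or died, and this may favour benefit.

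A reader might go further and say that the LCS result will be biased upward by a known number of points. The documents do not support that: they give neither expected PFS nor any relation between QOL and progression, and the ranges above only show what assumed values imply. The bias arises only if those who leave have a worse change; a worse level alone cancels in a paired difference.

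The consequence is confined to a secondary endpoint. No decision rule in Section 13.2 depends on QOL, and the response-rate conclusion is unaffected. The change is still worth making because a better analysis is available from scores already scheduled.

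**What to change.** Amend Section 13.3 as follows.

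1. Name baseline to month 3 as the single primary LCS contrast and treat later visits as descriptive. Month 3 is a recommendation: it is the earliest scheduled follow-up and loses the fewest patients. The documents do not dictate it.
2. Estimate change with a repeated-measures mixed model using all available scores. State explicitly that the questionnaire at documented progression enters the model, either assigned to its nearest scheduled visit or with time modelled continuously.
3. Keep the signed-rank test as a sensitivity analysis, and report the number of patients with both scores at each visit.
4. As a supportive summary only, report the proportion worsening by 3 or more LCS points, with and without counting progression or death as worsening.
5. State how missing forms are handled.

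The cost is plan wording: no new visits or questionnaires, provided the form at progression is completed as footnote 1 allows. The downside is reliance on missing-at-random data at n = 33. The model does not fully remove bias from death or unobserved decline, and the report should say so.
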